1 INTRODUCTION

Scleral contact lenses are rigid gas permeable (GP) lenses designed to rest on the sclera while vaulting over the cornea, with a fluid reservoir between the front surface of the cornea and the back surface of the lens. [1] The use of scleral contact lenses has become a standard, non-surgical management method in cases of corneal ectasia and ocular surface diseases.[2-4] Currently, the long-term impact that scleral contact lens wear has on the physiology of the pre-corneal tear film, cornea and limbus especially in dry eye (DE) patients, remains unknown.

Complaints of dryness and discomfort are common in contact lens wearers.[5-9] The use of scleral lenses to restore the integrity of the ocular surface in more severe dry eye has become increasingly accepted among eye care practitioners.[10-12] However, little is known about this treatment regimen and its impact on tear film structure in less severe cases. Therefore, there is a need for a study to determine the effectiveness of scleral contact lens wear in more typically encountered patients with DE complaints.

Understanding factors that influence tear film composition may aid in better understanding of the impact of scleral contact lenses on the health of the cornea. It is also worthy to note that questions regarding the potential impact of coated scleral contact lens designs incorporating Hydra-PEG (polyethylene glycol) technology produced by Tangible Science (Tangible Science LLC, Menlo Park, CA, USA) have not been addressed[13].

This study will provide valuable data on how scleral contact lens material, fit, and surface treatment impact the treatment of dry eye complaints.

2 PURPOSE AND HYPOTHESIS

The purpose of this study is to investigate the effects of scleral contact lens wear on a DE population using coated (Hydra-PEG) and uncoated (control) lenses. Symptoms of DE, quality of the tear film, quality of life, epithelial and overall corneal thickness, vision and comfort will be assessed before and after dispensing and wearing the lenses for four weeks.

The hypothesis is that **coated scleral contact lens wear is associated with improved ocular surface health in patients with dry eye disease (DED)**.

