3 OBJECTIVES

The specific objectives are:

1. To evaluate the impact of coated and non-coated scleral contact lenses on DE symptoms.
2. To assess the impact of the lenses on ocular surface health.
3. To measure the comfort and quality of life ratings of each lens type.
4. To determine the subjective ratings of each pair of lenses.

The primary outcome variables are:

1. Epithelial and corneal thickness
2. Quality of the tear film (osmolarity)
3. Levels of protease (inflammatory markers)
4. Contact Lens Impact on Quality of Life (CLIQ) questionnaire score
5. Contact Lens Questionnaire-8 (CLDEQ-8) questionnaire score

Other variables of interest:

- Hours of wear
- Subjective ratings of comfort, dryness, vision and burning.

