4 MATERIALS AND METHODS

4.1 STUDY DESIGN

4.1.1 OVERALL DESIGN

This will be a prospective, dispensing cross over study design involving five visits.

The first visit will involve screening, baseline measurements and trial fitting of scleral lenses. At this visit, participants may be wearing their habitual contact lenses (if any) as prescribed by their Optometrist/Ophthalmologist.

The second visit will be a dispensing visit of one of the pairs of the scleral contact lens designs (with or without Hydra-PEG, randomly assigned) and a single follow up visit after 8-10 hours of lens wear in a day, four weeks later (third visit). A washout period of a minimum of 48 hours will be applied between lens types. The fourth and fifth visits will be for the other scleral contact lens visits (delivery and after 4 weeks).

Scleral contact lenses to be worn in this study will be made of Boston XO material (with and without Hydra PEG) approved by Health Canada for commercial purposes. The scleral contact lenses will have a diameter of 14.8-15.4mm. The manufacturer's recommended guidelines will be used to select and fit these lenses, with an expected corneal clearance between 250 μ m to 350 μ m. As to which of the two scleral contact lenses are being assessed, both the investigator and the participant will be masked as the Optometric assistant will provide the lenses in an unlabelled case.

Masking the investigator will prevent bias when measuring the primary outcome variables and analyzing the data.

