4.4.1 SCREENING AND TRIAL FITTING

The investigator will determine participant eligibility by reviewing the inclusion and exclusion criteria. The diagnosis of dry eyes will also be confirmed by OSDI and SPEED questionnaires (self-assessed at home and confirmed on first appointment), osmolarity and levels of protease (using inflammandry test kit) in the tear film. Ineligible participants will be advised that they do not meet the criteria for the study. If eligible, then the trial scleral and soft contact lens fittings will be performed following the manufacturer's recommended guidelines.

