4.5 STUDY PROCEDURES

4.5.1 SCREENING AND BASELINE MEASUREMENTS

Screening & Baseline procedures: Participants will present to the screening visit. The cornea sagittal depth/height will be measured with the Visante OCT. OSDI and SPEED will be collected from the participant. Confirmation and change of dry eye status will be assessed based on tear

osmolarity and MMP-9 measurements using the Tearlab Osmolarity System and InflammaDry® test kits respectively. Additionally, their auto-refraction, visual acuity measurements as well as corneal topography with the Pentacam will be carried out. Eligibility will be confirmed, and a baseline biomicroscopy assessment will be performed to assess corneal. (Visit 0-0).

Ocular Surface Imaging: The eyes of the participants will be examined at the slit-lamp biomicroscope and imaged using the Keratograph® 5M. Participants will be seated at the Keratograph® 5M instrument and asked to blink 2-3 times and hold their eyes open for a few seconds until the instrument software takes a picture of the eye. This image acquisition will be repeated twice. This procedure will also be used to assess corneal and conjunctival staining. (Visits 0-0; 1-1; 2-2).

Fitting of the scleral lenses: Participants will be trial fitted with a scleral lens design using the Pentacam software and following the manufacturer's recommendation, but one pair will be ordered non-coated and the other pair will be Hydra-PEG coated (randomly selected). Acceptable fitting will be based on manufacturer's recommended guidelines for fitting these lenses. All scleral lenses used in the study will be made of Boston XO material. Participants will be instructed on insertion, removal, and proper handling of lenses (Visits 0-0, 1-1 2-1).

Imaging procedure With and Without Test Lenses: The anterior segment of the eye and the lens fit will be imaged and assessed using the Visante OCT, Keratograph 5M, Pentacam and Spectralis OCT prior to lens wear and after the lens delivery appointment (Visits 1-1, 2-1), and at the follow up appointment (Visits 1-2, 2-2).

Corneal Thickness Measurements: Corneal thickness will be measured with the Spectralis OCT and Pentacam before and after lens wear (Visits 0-0, 1-2, 2-2). Participants will be seated at the Spectralis OCT and the Pentacam instruments and to blink 2-3 times then hold their eye open for a few seconds until the instrument software takes a measurement of the corneal thickness. This measurement will be repeated twice.

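### The coating hypothesis names no comparator and is tied to no test, so an uncontrolled change from screening in osmolarity or MMP-9 could be reported as confirming it

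*Combined protocol and SAP*

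**What the plan says.** - **Hypothesis (Section 2).** "coated scleral contact lens wear is associated with improved ocular surface health", in people with dry eye disease. No comparator appears in the sentence. The purpose paragraph above it describes a study "using coated (Hydra-PEG) and uncoated (control) lenses", but also says that the outcomes "will be assessed before and after dispensing and wearing the lenses for four weeks".
- **Design (Section 4.1.1).** "This will be a prospective, dispensing cross over study design involving five visits", with lens order randomised and both investigator and participant masked. There is no follow-up period without a study lens.
- **Outcomes (Section 3).** Osmolarity and protease level are two of the five primary outcome variables.
- **Entry.** Section 4.4.1: "The diagnosis of dry eyes will also be confirmed by OSDI and SPEED questionnaires"; the sentence goes on to add osmolarity and protease. Section 4.4.2 also lists these two among the tools that determine eligibility. The inclusion list in Section 4.2.2 gives cut-offs for OSDI and SPEED and mentions neither marker.
- **Change (Section 4.5.1).** "Confirmation and change of dry eye status will be assessed based on tear" osmolarity and MMP-9. One sentence gives the same two measures both roles.
- **Schedule (Table 2).** Osmolarity and the InflammaDry MMP-9 test appear at Visit 0-0 and at follow-up Visits 1-2 and 2-2, but not at delivery Visits 1-1 and 2-1.
- **Analysis (Section 9.1, Table 3).** The parametric row, which includes osmolarity, lists a lens 1 versus lens 2 comparison and separate thickness and osmolarity comparisons, with paired t-test, ANOVA and RM-ANOVA. The nonparametric row, which holds protease, names a t-test and the Mann-Whitney test and no lens contrast.

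**The concern.** A hypothesis of improvement can be met in two ways: the coated lens does better than the uncoated one, or the coated lens does better than screening. Only the first isolates the coating. The second would be met equally well if both lenses improved by the same amount.

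The second reading also carries a bias. If people enter partly because a noisy reading was abnormal, their next reading will on average be closer to normal with no lens effect at all. Here the entry reading is also the only pre-lens value, so no second baseline absorbs that drift. At stake is a report that crediting the coating is justified when the data show only regression to the mean or a shared effect of scleral wear.

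**Working it through.** **The plan's own figure.** Section 4.2.1 gives 20 completers (25 enrolled), 90% power and type I error 0.05. It cannot be reproduced, because no effect size, SD value or endpoint is given. Enrolment fits a 20% loss: 20/(1 - 0.20) = 25. With n = 20 and a two-sided paired t-test, 90% power implies a standardised paired difference of 0.76. I take only n = 20 forward.

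**Assumptions, none from the documents.** Osmolarity is roughly normal with a higher reading worse. A share q of candidates passes a cut-off on the Visit 0-0 reading. Any two readings on one person correlate at r. Neither lens has an effect.

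**Expected spurious fall from screening**, in baseline SDs: (1 - r) × φ(c)/q, where c is the cut-off that a share q exceeds.
- q = 0.5: c = 0 and φ(c)/q = 0.399/0.5 = 0.798. So r = 0.7 gives 0.3 × 0.798 = 0.24, and r = 0.5 gives 0.40.
- q = 0.9: c = -1.28 and φ(c)/q = 0.1755/0.9 = 0.195. So r = 0.7 gives 0.06, and r = 0.5 gives 0.10.

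**Rejection rate** of a two-sided 5% paired t-test of follow-up against screening, n = 20, by simulation of null trials:

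| Share passing | r = 0.5: fall, rejection | r = 0.7: fall, rejection |
|---|---|---|
| 100% (no selection) | 0, 5% | 0, 5% |
| 90% | 0.10 SD, 7% | 0.06 SD, 6% |
| 70% | 0.25 SD, 20% | 0.15 SD, 13% |
| 50% | 0.40 SD, 45% | 0.24 SD, 28% |

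With r = 0.9 and half passing, the fall is 0.08 SD and the rate 12%. Tighter selection would give higher rates.

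**Hand check of one cell (q = 0.5, r = 0.7).** The variance of the selected screening reading is 1 - 0.798² = 0.363. The SD of the change is √(0.3² × 0.363 + 1 - 0.7²) = √0.543 = 0.737. The standardised change is 0.239/0.737 = 0.32, and the noncentrality is 0.32 × √20 = 1.45, which is consistent with 28%.

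**Same trials, coated against uncoated.** The uncoated lens appears to improve as often as the coated one (45% at q = 0.5, r = 0.5). The between-lens test rejects in 4.7% to 5.2% of trials in every setting, because the drift is common to both lenses and cancels.

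**MMP-9.** The table does not carry over, since Table 3 treats protease as nonparametric. As an illustration only, suppose that the reading is positive/negative and that all 20 enter positive, which the plan does not state. An exact McNemar test then needs 6 conversions (2 × 0.5⁶ = 0.031; 5 give 0.063). If 10%, 20%, 30% or 40% retest negative by chance, that happens with probability 1%, 20%, 58% or 87%.

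**Labels.** Table 1 numbers the lenses by order of delivery, each with or without coating. Read literally, lens 1 versus lens 2 in Table 3 is first against second, not coated against uncoated.

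**The case against.** Three stronger readings are tempting, and the documents support none of them.

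- **That the plan has no controlled comparison.** It has one. Section 2 calls the uncoated lens the control, Section 4.1.1 sets a masked crossover in randomised order, and Table 3 lists a lens comparison with a paired t-test in the row that includes osmolarity. What is missing is the link from the hypothesis to that comparison, and any lens contrast for protease.
- **That participants are selected for abnormal osmolarity or MMP-9.** Sections 4.4.1 and 4.4.2 say that the readings help to confirm diagnosis and eligibility. They give no threshold and do not say that a normal reading excludes anyone. Section 7 defines screening failure by Section 4.2.2, whose criteria name neither marker. Recruits must already be diagnosed with dry eye, so a high pass rate is plausible.
- **That the false-positive rate is 28-45%.** That is one end of an assumed range which starts at the nominal 5%. It concerns osmolarity only. Corneal and epithelial thickness, CLIQ and CLDEQ-8 are not entry criteria, so this argument does not reach them.

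It is also fair to object that change from baseline should not be banned. Section 1 states a need to learn how effective scleral lens wear is, and Section 3 asks about the impact of both lenses. That stands: such change may be reported, but not as evidence for the coating.

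Nor is the between-lens contrast free of assumptions. It needs negligible carryover. If order groups are unequal, a period effect also leaks in: with a 14:6 split and a shift of 0.5 SD of the paired difference, the bias is 0.5 × (14 - 6)/20 = 0.2 SD. Hence period belongs in the model.

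**Conclusion.** The point holds as a gap between hypothesis and analysis. Under the present wording, a fall from screening on the coated lens could be declared confirmation even if the control lens fell equally.

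The missing comparator matters whether or not there is selection, because a shared scleral-lens effect would be credited to the coating either way. The added bias from regression to the mean is real only so far as osmolarity and MMP-9 gate entry. For osmolarity, its effect on the before/after test runs from none (5%) through 6-7% at 90% passing to 28-45% at 50% passing, for r between 0.7 and 0.5. Pass rate and correlation are both assumptions, and no comparable figure can be fixed for MMP-9.

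**What to change.** 1. **Section 2.** State the hypothesis as coated compared with uncoated at four weeks.
2. **Section 9.1 and Table 3.** Name the within-person coated-minus-uncoated difference at Visits 1-2 and 2-2 as the test of the hypothesis, with period in the model. Write coated and uncoated in place of lens 1 and lens 2.
3. **Protease.** Add the same contrast to its row with a paired method suited to the scale, for example conditional logistic regression with period for a binary reading, or an ordinal crossover analysis. The Mann-Whitney test applied to the two sets of readings as independent samples ignores the pairing.
4. **Change from Visit 0-0.** Report it for each lens as secondary and uncontrolled, with a regression-to-the-mean caveat, and do not use it to confirm the coating hypothesis.
5. **Sections 4.2.2, 4.4.1 and 4.4.2.** Reconcile these on whether osmolarity and MMP-9 are gating criteria. If they are, record how many candidates fail on each, so that readers can judge the selection.

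The cost is wording in Sections 2, 4 and 9.1 and, at most, a screening count. No new visits, participants or measurements are needed.

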3 OBJECTIVES

The specific objectives are:

1. To evaluate the impact of coated and non-coated scleral contact lenses on DE symptoms.
2. To assess the impact of the lenses on ocular surface health.
3. To measure the comfort and quality of life ratings of each lens type.
4. To determine the subjective ratings of each pair of lenses.

The primary outcome variables are:

1. Epithelial and corneal thickness
2. Quality of the tear film (osmolarity)
3. Levels of protease (inflammatory markers)
4. Contact Lens Impact on Quality of Life (CLIQ) questionnaire score
5. Contact Lens Questionnaire-8 (CLDEQ-8) questionnaire score

Other variables of interest:

- Hours of wear
- Subjective ratings of comfort, dryness, vision and burning.

4 MATERIALS AND METHODS

4.1 STUDY DESIGN

4.1.1 OVERALL DESIGN

This will be a prospective, dispensing cross over study design involving five visits.

The first visit will involve screening, baseline measurements and trial fitting of scleral lenses. At this visit, participants may be wearing their habitual contact lenses (if any) as prescribed by their Optometrist/Ophthalmologist.

The second visit will be a dispensing visit of one of the pairs of the scleral contact lens designs (with or without Hydra-PEG, randomly assigned) and a single follow up visit after 8-10 hours of lens wear in a day, four weeks later (third visit). A washout period of a minimum of 48 hours will be applied between lens types. The fourth and fifth visits will be for the other scleral contact lens visits (delivery and after 4 weeks).

Scleral contact lenses to be worn in this study will be made of Boston XO material (with and without Hydra PEG) approved by Health Canada for commercial purposes. The scleral contact lenses will have a diameter of 14.8-15.4mm. The manufacturer's recommended guidelines will be used to select and fit these lenses, with an expected corneal clearance between 250 μ m to 350 μ m. As to which of the two scleral contact lenses are being assessed, both the investigator and the participant will be masked as the Optometric assistant will provide the lenses in an unlabelled case.

Masking the investigator will prevent bias when measuring the primary outcome variables and analyzing the data.

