4.2.2 NUMBER OF PARTICIPANTS

Recruitment: Participants who are patients of the University of Waterloo (UW) contact lens or ocular health clinics and those who are not UW patients but have previously participated in DE studies through CORE will be invited to participate in this study. With the patient's permission, the investigators will initiate recruitment according to the in-person script or flyers approved by the Office of Research Ethics (Appendices 1a-c). The investigators will discuss the project where any questions regarding the study procedures and any risks associated with the study can be answered. Eligibility will be determined using the inclusion and exclusion criteria. Current contact

lens wear of any lens type is not necessary for the DE participants. Informed consent will be obtained for all participants prior to their enrollment in the study (Appendix 2).

INCLUSION CRITERIA

A person is eligible for inclusion in the study if he/she:

- Is at least 18 years of age and has full legal capacity to volunteer.
- Has read, understood, and signed the information consent letter.
- Has been diagnosed with dry eyes.
- Has reduced tear break up time (NITBUT) and/or reduced tear meniscus height (TMH), clinical sign of dry eye disease and contact lens discomfort or is symptomatic of dry eye.
- Is willing and able to follow instructions and maintain the appointment schedule.
- Has greater than 13 points on the OSDI.
- Has greater than 4 points on the Standardized Patient Evaluation of Eye Dryness (SPEED).

EXCLUSION CRITERIA

A person will be excluded from the study if he/she:

- Is using any topical medications that will likely affect the study outcome.
- Has undergone any form of corneal surgery.
- Has any known allergies or sensitivity to the diagnostic pharmaceuticals or products, such as fluorescein, used in this study.
- Has persistent, clinically significant corneal or conjunctival staining using sodium fluorescein dye not related to the signs of dry eye.
- Has any clinically significant lid or conjunctival abnormalities and active neovascularization on the cornea.
- Anatomic variations of the conjunctiva that can impair proper scleral or soft contact lens wear/fitting
- Ocular pathology other than dry eye (e.g. glaucoma, macular degeneration) which may significantly impact visual function and assessment.
- Is participating in any other type of eye related clinical or research study.

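### Change from Visit 0-0 in thickness, osmolarity and MMP-9 is partly confounded with time of day and habitual lens wear; the coated-versus-uncoated contrast is not

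*Combined protocol and SAP*

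**What the plan says.** **Aim.** Section 2 lists the outcomes, including thickness, and says they "will be assessed before and after dispensing and wearing the lenses for four weeks". Section 4.5.1 schedules corneal thickness "before and after lens wear (Visits 0-0, 1-2, 2-2"), uses osmolarity and MMP-9 to follow change in dry eye status, and Section 4.3.8 takes the screening tear sample as the baseline for the tear assays.

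**Baseline conditions.** Of Visit 0-0, Section 4.1.1 says: "At this visit, participants may be wearing their habitual contact lenses (if any"). Section 4.2.2 adds that current "lens wear of any lens type is not necessary for the DE participants", so the baseline sample can mix wearers and non-wearers. No time of day is set. The 48-hour minimum washout in Sections 4.1.1 and 4.4.2 lies between the two study lenses; nothing comparable precedes Visit 0-0.

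**Follow-up conditions.** Each lens has "a single follow up visit after 8-10 hours of lens wear in a day", four weeks after dispensing.

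**Other pre-lens readings.** Section 4.5.1 also plans imaging by "Spectralis OCT prior to lens wear and after the lens delivery appointment (Visits 1-1, 2-1"). That covers imaging only. No clock time is set, it is not named as the baseline, and the delivery-visit rows of Table 2 list Spectralis only for lens fit after insertion.

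**Analysis.** Table 3 in Section 9.1 has no adjustment for time of day or prior lens wear.

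**The concern.** A before/after change can be read as an effect of the lens only if the two readings are taken under comparable conditions apart from the lens. Here two other things can differ. One is clock time: follow-up is pushed late in the day by the wear requirement, while baseline may fall at any hour. The other is habitual lens wear: some participants may have just removed their own lenses when baseline is read, and others will have worn none.

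The plan treats recent lens wear as something to clear between study lenses, but does not apply that reasoning to the baseline. There is no untreated arm, so Visit 0-0 is the only reading of osmolarity and MMP-9 without a study lens. Randomising lens order cannot remove a shift common to both lenses. What is at stake is any statement that the lenses improved or worsened thickness, osmolarity or MMP-9 relative to baseline.

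**Working it through.** **1. Visits side by side**

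| | Visit 0-0 | Visits 1-2 and 2-2 |
|---|---|---|
| Clock time | not set | normally late in the day |
| Habitual lenses | allowed, optional | replaced by the study lens |
| Lens-free interval before | none stated | not applicable (wear is the exposure) |
| Thickness, osmolarity, MMP-9 | yes | yes |
| Comfort, CLDEQ-8, CLIQ in Table 2 | none | collected for each lens |

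**2. What is biased and what is not.** Let λ1 and λ2 be the true mean changes due to lenses 1 and 2, and c the mean shift from clock time and habitual wear.

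- Expected change from Visit 0-0 with lens k: λk + c. If λk = 0, the expected change is c, not 0.
- Expected difference between lenses: (λ1 + c) − (λ2 + c) = λ1 − λ2. The shift cancels, because both lenses share the same baseline and the same follow-up conditions.

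**3. Inputs.** n = 20 completers and type I error 0.05 (Section 4.2.1; two-sided is my assumption, as sidedness is not stated). Section 4.2.1 gives neither an SD nor an effect size, and no document gives a diurnal or habitual-lens effect. So c cannot be put in measurement units and the sample size cannot be reproduced. I express c as b SDs of the paired change and show a range.

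**4. False-positive rate of a paired t-test when λ = 0.** Degrees of freedom 19, critical value 2.093, noncentrality b × √20. The rate is P(|T| > 2.093) under the noncentral t.

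| Assumed b | b × √20 | False before/after finding |
|---|---|---|
| 0 | 0 | 5.0% |
| 0.1 | 0.447 | 7.1% |
| 0.2 | 0.894 | 13.6% |
| 0.3 | 1.342 | 24.7% |
| 0.5 | 2.236 | 56.5% |

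**5. Scale.** With n = 20, 90% power and two-sided 0.05, the noncentral t back-solves to a detectable paired difference of 0.76 SD. A shift of 0.5 SD would be 0.5 / 0.76 = 0.66 of that.

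**6. If only habitual wearers are affected.** Suppose 30% of participants carry a 0.5 SD shift and the rest none. The mean is 0.30 × 0.5 = 0.15 SD, and the rate is 9.8%, ignoring the added variance. The 30% is an assumption.

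The rates apply to outcomes analysed by a paired t-test, such as thickness and osmolarity. Table 3 puts protease levels in the nonparametric row, so for MMP-9 the argument in step 2 holds but these percentages do not carry over directly.

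**The case against.** The strongest reply is that this is a randomised, masked crossover whose hypothesis concerns coated lenses, and that Table 3 names a paired comparison of lenses 1 and 2. Step 2 shows that contrast is untouched. Table 3 also never defines a test of change from Visit 0-0, so the paired test in step 4 is an illustration. Both points stand and limit the scope. They do not dispose of the point, because Section 2 states a before/after assessment, Section 4.5.1 ties thickness to Visit 0-0, and Table 3 lists thickness and osmolarity comparisons and RM-ANOVA beyond the lens comparison.

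Second, the pre-lens imaging at Visits 1-1 and 2-1 could supply a better thickness reference, and Visit 2-1 follows the 48-hour washout. This is a partial remedy for thickness, available only if the plan names it and fixes its conditions. It does not reach osmolarity or MMP-9.

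Third, the shift may be small. Visit 0-0 is unscheduled, not fixed in the morning, and habitual wear may concern few people. That stands: at 0.1 SD the rate is 7.1%, and the percentages show sensitivity, not demonstrated bias.

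Three stronger readings are tempting.
- A reader might infer that comfort is affected, since Section 2 lists it. Table 2 schedules no comfort rating, CLDEQ-8 or CLIQ at Visit 0-0, and the ratings in Section 4.3.11 are for the study lenses.
- A reader might count the 8-10 hours of study-lens wear as a confounder. It is the exposure under study; only clock time and habitual wear at baseline qualify.
- A reader might conclude that no part of the change can be credited to the lens. The documents support partial confounding of unknown size, not that.

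**Conclusion.** The point holds in limited form. As written, the plan allows change from Visit 0-0 in corneal and epithelial thickness, osmolarity and MMP-9 to include a shift from time of day and habitual lens wear. The randomised coated-versus-uncoated difference is not biased by it.

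The size is unknown. Over an assumed shift of 0.1 to 0.5 SD of the paired change, the false before/after rate runs from about 7% to 56% against a nominal 5%. This rests on 20 completers, a two-sided 0.05 paired t-test, and a shift that is systematic across participants.

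Matching conditions would not turn the before/after change into a controlled comparison. There is still no untreated arm, and under Section 4.3.8 the tear assays compare ocular-surface fluid at baseline with lens-bowl fluid later, which clock matching does not cure. This is a cheap improvement to a stated aim, not a threat to the main contrast.

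**What to change.** In Sections 4.1.1 and 4.5.1:

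1. Take the baseline readings in the same clock-time window as that participant's follow-ups, and hold Visits 1-2 and 2-2 at the same clock time within participant. The latter removes noise from the lens contrast too.
2. For habitual wearers, take baseline readings after the protocol's own 48-hour lens-free interval. Table 2 places consent at Visit 0-0, so consent must be obtained before that instruction is given. The at-home OSDI and SPEED step in Section 4.4.1 shows that contact before the visit already exists. For thickness only, the alternative is to name the pre-lens imaging at Visit 1-1 as the baseline, after such an interval, and add it to the delivery rows of Table 2.
3. Record clock time and same-day habitual lens wear at Visit 0-0, and clock time at every later visit. Hours of wear is already a listed variable in Section 3.

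In Section 9.1, state that the coated-versus-uncoated difference is the main inference and that change from baseline is uncontrolled, including the difference in tear source.

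The cost is less booking flexibility, notably for the 2.5-hour Visit 0-0, a short lens-free period for habitual wearers, and an earlier consent step where that route is used. No extra visits are needed and no sample-size figure changes.
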